7. DISCONTINUATION OF STUDY INTERVENTION AND PARTICIPANT DISCONTINUATION/WITHDRAWAL

7.1. Discontinuation of Study Intervention

A participant's study intervention must be discontinued if:

- The participant withdraws consent to receive study intervention.
- The investigator believes that for safety reasons or tolerability reasons (eg, AE) it is in the best interest of the participant to discontinue study intervention.
- The investigator or sponsor believes that there are no further benefit of continuing the study for the participants.
- The participant becomes pregnant or planning to become pregnant while enrolled in this study or within 12 weeks after the last administration of study intervention.
- Noncompliance with study intervention administration.
- The participant initiates treatment with prohibited therapies listed in Section 6.8 unless agreed upon with the sponsor medical monitor.

• The participant is deemed ineligible according to the following TB screening criteria:

A diagnosis of active TB is made.

A participant has symptoms suggestive of active TB based on follow-up assessment questions and/or physical examination or has had recent close contact with a person with active TB and cannot or will not continue to undergo additional evaluation.

A participant undergoing evaluation has a chest radiograph or chest CT with evidence of current active TB and/or a positive QuantiFERON-TB test or T-SPOT test result, unless active TB can be ruled out and appropriate treatment for latent TB can be initiated prior to the next study intervention administration and continued to completion (see also Section 8.2.9). Indeterminate QuantiFERON-TB test or borderline T-SPOT results should be handled as in Section 8.2.9. Participants with persistently indeterminate QuantiFERON-TB test results or borderline T-SPOT may continue without treatment for latent TB if active TB is ruled out, their chest radiograph or chest CT shows no abnormality suggestive of TB (active or old, inactive TB) and the participant has no additional risk factors for TB as determined by the investigator. This determination must be promptly reported to the sponsor and recorded in the participant's source documents and initialed by the investigator.

A participant receiving treatment for latent TB discontinues this treatment prematurely or is noncompliant with the therapy.

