5.1.2. Missing Data

Unless otherwise specified, a missing-at-random (MAR) missing data mechanism is assumed for all efficacy endpoints and there will be no imputation of missing data prior to the analysis.

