5.2. Participant Dispositions

Screened participants and the number of screen failures will be summarized overall in all enrolled participants.

The number of participants in the following disposition categories will be summarized in the main study period and LTE period by intervention group and overall:

- Participants randomized
- Participants who received study intervention
- Participants who completed the study
- Participants who discontinued study intervention
- Reasons for discontinuation of study intervention
- Participants who terminated study prematurely
- Reasons for termination of study

Listings of participants will be provided for the following categories:

- Participants who discontinued study intervention
- Participants who terminated study prematurely

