Change from baseline in digital ulcer counts at Week 24	Difference in LSMs of change from baseline in digital ulcer counts at Week 24 between guselkumab vs placebo
Change from baseline in digital ulcer counts at Week 52	Difference in LSMs of change from baseline in digital ulcer counts at Week 52 between guselkumab vs placebo
Change from baseline in HAQ-DI score at Week 24	Difference in LSMs of change from baseline in HAQ-DI score at Week 24 between guselkumab vs placebo
Change from baseline in HAQ-DI score at Week 52	Difference in LSMs of change from baseline in HAQ-DI score at Week 52 between guselkumab vs placebo

Intercurrent events and their corresponding strategies:

The intercurrent events for all key secondary endpoints at Week 24 are the same as those in the primary estimand, as follows:

1. A prohibited change in SSc medication (for details, see [Appendix 11](#))
2. Discontinuation of study intervention due to lack of efficacy or an AE of Systemic Sclerosis

As rescue medication is available for participants after Week 24, an additional intercurrent event is defined for secondary efficacy endpoints at Week 52.

3. Initiation of rescue medication after Week 24

Intercurrent events 1, 2 and 3 are all handled by the **composite strategy** to assume that the occurrence of intercurrent events indicates an unfavorable outcome. For continuous endpoints, the change from baseline will be zero; and for binary endpoints, the participants are considered as not achieving an improvement (ACR CRISS score ≥ 0.6) or experiencing worsening (an increase from baseline ≥ 5 points and $\geq 20\%$ in mRSS).

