5.4.2.3. Analysis Methods

For continuous endpoint as change from baseline in mRSS at Week 52, an MMRM model with treatment group, baseline mRSS, stratification factors (presence of ILD [yes, no] and baseline anti-topoisomerase I antibody status [positive, negative]), visit, treatment group by visit interaction, and baseline mRSS by visit interaction as fixed effects will be applied. The estimates of the treatment difference between guselkumab and placebo will be provided by the difference in the least squares means (LSMs), as well as the 2-sided 80% and 95% CIs for the differences and p-values.

For continuous endpoints other than change from baseline in mRSS at Week 52, an MMRM model with treatment group, baseline value of the endpoint, stratification factors (presence of ILD [yes, no], baseline mRSS (low [≥ 10 to ≤ 15], high [≥ 16 to ≤ 22]) and baseline anti-topoisomerase I antibody status [positive, negative]), visit, treatment group by visit interaction, and baseline value of the endpoint by visit interaction as fixed effects will be applied. The estimates of the treatment difference between guselkumab and placebo will be provided by the difference in the least squares means (LSMs), as well as the 2-sided 80% and 95% CIs for the differences and p-values. The degree of freedom will be calculated as the error degrees of freedom for the model minus the number of extra random effects estimated.

An unstructured covariance matrix for repeated measures within a participant will be used. In case of lack of convergence, empirical structured covariances will be used in the following order until convergence is reached: 1) Toeplitz 2) first order Autoregressive Moving Average. If the normality assumption is in question, an appropriate transformation will be used.

For binary endpoints such as proportion of participants achieving an ACR CRISS score of 0.6, a logistic regression model that includes factors for treatment group and stratification factors (presence of ILD [yes, no], baseline mRSS (low [≥ 10 to ≤ 15] or high [≥ 16 to ≤ 22]) and baseline anti-topoisomerase I antibody status [positive, negative]) will be applied provide the odds ratios, p-values, as well as the 2-sided 80% and 95% CIs for comparisons between guselkumab and placebo.

5.4.2.4. Supplementary Analysis for Change from Baseline in MRSS at Week 52

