5.5.2. Analysis Methods

The analyses of exploratory efficacy endpoints will be based on the FAS.

Descriptive statistics, such as n, mean, SD, median, IQ range, minimum and maximum for continuous variables and counts and percentages for discrete variables will be used to summarize data when applicable. The analysis will be based on the observed data; therefore, no imputation of missing data will be performed.

All statistical testing will be performed between treatment groups at the 2-sided 0.2 significance level.

Continuous efficacy endpoints collected at multiple post baseline time points (ie, the endpoints of change from baseline) will be compared using a MMRM model. The model will include all available data through Week 24 (for endpoints at Week 24) or through Week 52 (for endpoints at Week 52).

The explanatory variables of the MMRM model will include treatment group, baseline value of the endpoint, stratification factors (presence of ILD, baseline mRSS and baseline anti-topoisomerase I antibody status), visit, treatment group by visit interaction, and baseline value of the endpoint by visit interaction as fixed effects. The estimates of the treatment difference between treatment groups will be provided by the difference in LSMs. The 80% CI for the differences in LSMs will be calculated based on the MMRM.

The analysis of change from baseline in fibrotic change assessed with HRCT at Week 24 and nailfold capillaries change at Week 24 will be performed using ANCOVA (analysis of covariance) model with baseline value of the endpoint as covariate, and stratification factors (presence of ILD, baseline mRSS and baseline anti-topoisomerase I antibody status) and treatment group as factors.

A logistic regression model will be used to compare the proportion of participants achieving selected endpoints (eg, worsening of % predicted FVC) between guselkumab and placebo. The analyses will include treatment group, stratification factors (presence of ILD, baseline mRSS and baseline anti-topoisomerase I antibody status) as factors. The same intercurrent events and composite strategy defined in Section 5.4.2.2 will be applied to following endpoints as well:

- The proportion of participants who experience FVC decline compared with baseline through Week 52
- The proportion of participants who experience worsening of FVC through Week 52

A summary of baseline values and change from baseline at Week 24 and Week 52 will be presented for nailfold capillaroscopy.

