As to time to event endpoint, ie, time to disease worsening, it will be summarized by Kaplan-Meier method, with the median, 25th, and 75th percentiles and 95% CI for the quartiles. The comparison between guselkumab and placebo will use a Cox proportional hazards model adjusting for the stratification factors at randomization. An 80% CI for the hazard ratio (HR) will be produced. The

same intercurrent events and handling strategy defined in Section [5.4.2.2](#) will be applied to this endpoint as well, the detailed definition of censoring and event is described as below:

No.	Situation	Date of Event or Censoring	Outcome
1	Disease worsening: an increase from baseline ≥ 5 and $\geq 20\%$ in mRSS or decrease $>10\%$ from baseline in FVC %	First occurrence of disease worsening	Event
2	A prohibited change in SSc medication on or before Week 52	First occurrence of prohibited change	Event
3	Discontinuation of study intervention due to lack of efficacy or an AE of SSc before Week 52	Date of discontinuation of study intervention	Event
4	Initiation of rescue medication after Week 24 and through Week 52	Date of initiation of rescue medication	Event
5	Other	Date of last mRSS or FVC assessment through Week 52	Censored

Note: if participants had more than one items of 1,2,3,4 occurred, the date of first occurrence will be considered as event date.

Unless otherwise specified, LTE efficacy endpoints will only be summarized using descriptive statistics.

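### Time to disease worsening censors a death with no earlier listed event, and the binary efficacy endpoints have no rule for death

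*SAP*

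**What the plan says.** **Time to disease worsening (exploratory).** The table in SAP 5.5.2 has four event rows: measured worsening on mRSS or FVC, a prohibited change in SSc medication, stopping study intervention for lack of efficacy or an AE of SSc, and rescue after Week 24. Row 5, headed Other, censors everyone else at "Date of last mRSS or FVC assessment through Week 52".

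**Binary endpoints.** SAP 5.4.2.2 assigns an unfavourable outcome after the listed intercurrent events: "for binary endpoints, the participants are considered as not achieving an improvement", or are counted as worsened. The listed events are a prohibited medication change, discontinuation for lack of efficacy or an AE of SSc, and, for Week 52, rescue. SAP 5.5.2 carries the same events and strategy over to FVC decline and to "The proportion of participants who experience worsening of FVC through Week 52". The analysis in 5.4.2.3 is "a logistic regression model that includes factors for treatment group and stratification factors", with no rule for a missing response.

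**Missing data.** SAP 5.1.2: "a missing-at-random (MAR) missing data mechanism is assumed for all efficacy endpoints and there will be no imputation of missing data". For the exploratory endpoints, 5.5.2 adds: "The analysis will be based on the observed data; therefore, no imputation of missing data will be performed".

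**Death.** It appears in none of the intercurrent-event lists (5.3.2, 5.4.2.2, Appendix 11), is not an ACR CRISS Step 1 condition (5.4.2.1), and is not an event row in 5.5.2. SAP 5.7.2 summarises deaths with cause and relationship, and lists them, as safety data. Protocol 7.2 gives death as a reason for withdrawal from the study.

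**The concern.** The SAP has chosen a composite approach: stopping drug for SSc reasons, switching to a prohibited medication or needing rescue is counted as failure. Death is a worse outcome than any of these, yet it has no place in the composite.

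In time to worsening, censoring treats a participant who died as having the same later risk of worsening as those still under observation. That is doubtful here. The protocol's introduction names pulmonary involvement as the most common cause of death in SSc, and lung function is scheduled only at Weeks 12, 24 and 52 after screening (plus early termination). A fatal decline between Weeks 24 and 52 could leave no FVC on record after Week 24.

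In the binary analyses, removing a participant who died takes a failure out of both numerator and denominator, so that arm's failure proportion falls. The secondary p-values are nominal (SAP 5.4.1), but the secondary-endpoint confidence intervals are a stated reference for the internal go/no-go decision (SAP 5.1.1).

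**Working it through.** **1. Following one participant through the rules.** Suppose a participant dies at Week 30 with no measured worsening, prohibited medication, rescue or SSc-related discontinuation.
- Time to worsening: rows 1 to 4 do not apply, so row 5 does. The time is censored at the last mRSS or FVC assessment.
- Week 52 binary endpoints: no intercurrent event and no Week 52 value. Nothing is imputed and the model has no missing-response rule, so there is no response to enter. This step is inferred.
- Week 24 binary endpoints: the Week 24 value exists, so nothing changes.

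**2. How many deaths.** The plan gives no figure. I use the 84% five-year dcSSc survival of the more recent cohort in Protocol section 2, assume a constant hazard, and scale it by h because eligibility excludes severe disease (h is an assumption).

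Death probability per participant: p = 1 − 0.84^(h·t/5), with t = weeks/52.18 in years. Expected deaths are 56p. The chance of at least two in a given arm is Binomial(28, p).

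| h | Week | p | Expected among 56 | No death among 56 | ≥2 in a given arm |
|---|---|---|---|---|---|
| 1 | 24 | 0.0159 | 0.9 | 41% | 7% |
| 1 | 52 | 0.0342 | 1.9 | 14% | 25% |
| 0.5 | 24 | 0.0080 | 0.4 | 64% | 2% |
| 0.5 | 52 | 0.0172 | 1.0 | 38% | 8% |
| 0.25 | 24 | 0.0040 | 0.2 | 80% | 0.6% |
| 0.25 | 52 | 0.0086 | 0.5 | 61% | 2% |

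The older cohort's 69% would give about 4.0 deaths in a year (56 × 0.0715), but the protocol itself says survival has since improved. At any given hazard these figures overstate the problem, because some deaths will follow a listed event.

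**3. Illustrative mRSS-worsening counts.** With the SAP's SD of 8 and difference of −4.7, and an assumed mean placebo change m, the expected counts per 28 are 28·P(N(m, 8) ≥ 5) for placebo and 28·P(N(m − 4.7, 8) ≥ 5) for guselkumab. The 20% condition adds nothing, because 5/22 = 23% at the highest eligible baseline. Results, placebo v guselkumab: m = −2, 5.3 v 2.0; m = 0, 7.4 v 3.2; m = +2, 9.9 v 4.7. I round these to 5 v 2, 7 v 3 and 10 v 5, and add an assumed 12 v 8 because composite failures also count.

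**4. Death left out or counted.** Unadjusted odds ratios, guselkumab v placebo. The shift is on the log scale, divided by the SE of the left-out estimate.

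| Base (placebo v guselkumab) | Deaths | Left out | Counted as worsening | Shift |
|---|---|---|---|---|
| 7 v 3 | 1 guselkumab | 3/27 v 7/28: 0.38 | 4/28 v 7/28: 0.50 | 0.288/0.752 = 0.4 SE |
| 7 v 3 | 1 placebo | 3/28 v 7/27: 0.34 | 3/28 v 8/28: 0.30 | −0.134/0.752 = −0.2 SE |
| 7 v 3 | 1 in each arm | 3/27 v 7/27: 0.36 | 4/28 v 8/28: 0.42 | 0.154/0.754 = 0.2 SE |
| 7 v 3 | 2 guselkumab | 3/26 v 7/28: 0.39 | 5/28 v 7/28: 0.65 | 0.511/0.753 = 0.7 SE |
| 5 v 2 | 1 guselkumab | 2/27 v 5/28: 0.37 | 3/28 v 5/28: 0.55 | 0.405/0.885 = 0.5 SE |
| 10 v 5 | 1 guselkumab | 5/27 v 10/28: 0.41 | 6/28 v 10/28: 0.49 | 0.182/0.633 = 0.3 SE |
| 12 v 8 | 1 guselkumab | 8/27 v 12/28: 0.56 | 9/28 v 12/28: 0.63 | 0.118/0.569 = 0.2 SE |

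In the first row the unadjusted 80% interval moves from 0.14–0.98 to 0.21–1.22, so it comes to include 1. That depends on the chosen counts: with 5 v 2 or 12 v 8 it includes 1 either way.

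For ACR CRISS with an assumed 10 responders of 28, leaving out one death changes the response only from 10/28 = 36% to 10/27 = 37%.

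**The case against.** A reader might infer that the SAP is silent on death throughout. It is not. Row 5 is a stated catch-all for time to worsening, and deaths are tabulated and listed as safety data. Only the binary endpoints lack a rule, and dropping the participant there is an inference from other sections.

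A reader might also infer that every death is lost. That goes too far. Protocol 10.4.5 makes the cause of a death within 12 weeks of the last dose an SAE, an AE is a permitted reason for stopping treatment (Protocol 7.1), and SAP 5.2 tabulates "Reasons for discontinuation of study intervention" separately from reasons for leaving the study. A fatal SSc event may therefore already count through the SSc-AE discontinuation rule. Earlier worsening, rescue or a Step 1 condition will capture others. What stands is that the SAP does not say so, and the answer depends on what the site records.

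The strongest defence is that the protocol defines time to worsening by mRSS and FVC alone, so censoring at death estimates a cause-specific hazard. That would carry more weight if rows 2 to 4 had not already made the endpoint a composite of worsening and treatment failure.

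It is also true that loss to follow-up, withdrawal of consent and other AEs leave missing binary responses without a rule. The change below does not cure that. Counting death as failure in the binary analyses while the MMRM assigns it no value is a further, acceptable inconsistency: death has no natural mRSS value.

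**Conclusion.** The point holds, and it is small. Under the written table, a death with no earlier row 1 to 4 event is censored. For the binary endpoints, a death before the endpoint visit most plausibly removes the participant, to the advantage of the arm concerned.

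On the assumed hazards, about 0 to 2 deaths would be expected among 56 by Week 52, and there may be none. One guselkumab death shifts the illustrative log odds ratio by about 0.2 to 0.5 SE. The 0.7 SE case needs two guselkumab deaths and no placebo death: by Week 52 that has a chance of about 9% at the full hazard (0.248 × 0.378) and 5% at half (0.084 × 0.615). The event counts and hazards are assumptions, and the odds ratios are unadjusted.

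The documents do not support reading this as a threat to the primary result. The primary analysis is an MMRM of mRSS change at Week 24, by when 0.2 to 0.9 deaths are expected. Nor does it show that a go/no-go conclusion would change.

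**What to change.** Before the Week 52 database lock, while the blind still holds:

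1. Add a row to the SAP 5.5.2 table: *Death on or before Week 52; date of death; Event*. Include it in the table's note on taking the earliest event.
2. In SAP 5.4.2.2, and for the FVC binary endpoints in 5.5.2, count death on or before the endpoint visit as non-response for ACR CRISS and as worsening (or decline) for the others.
3. Add a sensitivity analysis in which only SSc-related deaths count as failures, with other deaths handled as now planned.
4. Record the change in SAP Appendix 2.

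Leave the MMRM analyses as planned.

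The cost is one table row, one sentence for each set of binary endpoints and one small analysis. Deaths and their causes are already collected. The downside is that deaths unrelated to SSc become failures in the main binary and time-to-event analyses, which the sensitivity analysis addresses, and that time to worsening then goes beyond the protocol's mRSS and FVC definition, hence the Appendix 2 entry.

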5.6. Other Efficacy Analyses

Descriptive statistics of primary, secondary and exploratory efficacy endpoints will be provided by study intervention at each scheduled visit through week 24/52/76/104 if applicable. These endpoints will be analyzed by the method described in Section [5.3.3](#), [5.4.2.3](#) and [5.5.2](#) respectively.

LS mean and standard error of LS mean, together with the LS mean difference between treatment groups will be calculated for the continuous endpoints, while for the binary endpoints, the odds ratio will be calculated.

Listings of primary, secondary and exploratory efficacy endpoints will be provided.

5.7. Safety Analyses

All safety analyses will be based on the safety analysis set and presented by actual intervention received, unless otherwise specified.

For all continuous safety variables, descriptive statistics by intervention group will include the N, mean, standard deviation, median, minimum, and maximum. Categorical variables will be summarized by intervention group using frequency counts and percentages.

5.7.1. Extent of Exposure

The number and percentage of participants who receive study interventions will be summarized by visit.

Descriptive statistics for duration of study interventions will be summarized. Study intervention duration (weeks) is defined as ((date of last dose of study intervention – date of first dose of study intervention) +1)/7.

For IV doses, the number (%) of participants with a study intervention modification during the infusion will be summarized by intervention group and visit.

Descriptive statistics will be presented for the following parameters:

- Number of administrations
- Cumulative total dose

Intervention compliance will be summarized descriptively. See [Appendix 7](#) for further details.

5.7.2. Adverse Events

The verbatim terms used in the CRF by investigators to identify adverse events will be coded using the Medical Dictionary for Regulatory Activities (MedDRA). Any AE occurring at or after the initial administration of study intervention is considered to be treatment emergent. If the event occurs on the day of the initial administration of study intervention, and either event time or time of administration are missing, then the event will be assumed to be treatment emergent. If the event date is recorded as partial or completely missing, then the event will be considered to be treatment emergent unless it is known to be prior to the first administration of study intervention based on partial onset date or resolution date. All reported treatment-emergent adverse events will be included in the analysis. For each adverse event, the number and percentage of participants who experience at least 1 occurrence of the given event will be summarized by intervention group.

Summary tables will be provided for treatment-emergent adverse events in the main study period and LTE period:

- AEs
- Serious AEs (SAEs)
- AEs leading to discontinuation of study intervention
- AEs by severity
- AEs by relationship to study intervention
- AEs leading to drug interruption

- Infusion reaction
- Injection site reaction
- Covid-19 related AEs and SAEs

In addition to the summary tables, listings will be provided for participants who:

- Had SAEs
- Had AEs leading to discontinuation of study intervention

Incidence of other treatment-emergent adverse events of special interest will be summarized. See [Appendix 8](#) for list of adverse events in each category.

Deaths will be displayed by actual intervention received. Frequencies for the following parameters will be included in the summary table:

- Number of participants who died
- Cause of death
- Relationship to study intervention (yes/no)

A listing of participants who died will be provided.

